9.2.2 Exclusion criteria

1. Patients age < 18 years
2. Patients with diagnosis of other types of diabetes than T2D
3. Patients who do not provide written consent to the terms of the study

9.3 VARIABLES

The following parameters will be collected and assessed at study index date 1:

1. Patient demographics (age, gender, height, weight, BMI, ethnicity)
2. Time since diagnosis of Type 2 Diabetes
3. Clinical parameters relevant for T2D, CVD, CKD assessment (see below) as valid on study index date 1
4. Comorbidities like cardiovascular disease and related risk factors (see below) and Comorbidities like chronic kidney disease and related risk factors (see below) at study index date 1
5. T2D medication the treating physician newly prescribes at study index date 1
6. Concomitant T2D medications at study index date 1
7. Concomitant CVD and CKD medications at index date 1
8. Involvement of other HCPs in treatment decisions at study index date 1
9. Relevant socioeconomic parameters (see below) at index date 1

The following parameters will be collected and assessed at study index date 2 (= approximately one year ± 2 months after index date 1):

1. Status of T2D medication (continuation / discontinuation)
2. If discontinuation:
 - a. stop date of initial(index date 1) T2D medication (if available)
 - b. Reason for therapy discontinuation (see below)
 - c. Involvement of other HCPs in decision for therapy discontinuation

9.3.1 Exposures

Exposure to each treatment of interest is defined as having received a first prescription of the treatment of interest between September and December 2018.

9.3.2 Outcomes

1. Patient demographics:

- age
- gender
- height
- weight
- BMI
- Ethnicity*

*assessment of ethnicity (black or non-black) necessary for calculation of eGFR

2. Time since diagnosis of Type 2 Diabetes (years)

3. Clinical parameters relevant for T2D, CVD, CKD assessment (last available and date when it was collected) as valid on study index date 1

- T2D
 - HbA1c (numeric value)
- CVD
 - Blood pressure (numeric value for systolic and diastolic blood pressure)
 - LVEF (numeric value and info on whether an Echo was performed)
 - Blood lipids (numeric values for total cholesterol, LDL, HDL, and triglycerides)
- CKD
 - Serum creatinine (numeric value)
 - eGFR (calculated for analysis according to the CKD-EPI formula considering serum creatinine level, gender, age, and ethnicity)
 - UACR (numeric value)

4. Prevalence of comorbidities and related risk factors for CVD, CKD at index date 1

- Comorbidities
 - History of acute myocardial infarction (yes/no)
 - History of cardiology intervention (such as Percutaneous Coronary Intervention (PCI), Coronary Artery Bypass Grafting (CABG)) (yes/no)
 - Ischemic heart disease (defined as coronary artery disease, angina) (yes/no)
 - Heart failure (yes/no)
 - Confirmed by echocardiography (yes/no)
 - History of stroke (yes/no)

- Peripheral arterial disease (including limb angioplasty, stenting, bypass surgery, amputation, significant peripheral artery stenosis,) (yes/no)
- Risk factors
 - Being overweight (BMI ≥ 25 to <30) (yes/no) or obese (BMI ≥ 30) (yes/no) according to the WHO criteria (26)
 - Hypertension (defined as systolic blood pressure ≥ 140 mmHg and / or diastolic blood pressure ≥ 90 mmHg) (y/n)
 - 10-year Risk for fatal CVD according to the applying SCORE Risk Chart (European Society of Cardiology) taking into account patient's age, gender, systolic blood pressure, smoking status, and total cholesterol value at index date.
 - Tobacco smoking (current smoker/ ex-smoker/ never smoker)
 - Being physically inactive (defined as less than 2.5 hours of moderate-intensity aerobic exercise or less than 75 minutes of vigorous aerobic exercise per week) (yes/no)
 - Having a family history of early heart disease (yes/no)
 - Having a family history of early kidney disease (yes/no)

5. T2D medication the treating physician newly prescribes at study index date 1 and reason for the choice

- SGLT2i
 - canagliflozin
 - dapagliflozin
 - empagliflozin
 - ertugliflozin
- DPP4i
 - alogliptin
 - linagliptin
 - sitagliptin
 - saxagliptin
 - vildagliptin
- GLP1a
 - dulaglutide
 - exenatide
 - liraglutide
 - semaglutide
 - lixisenatide
- Reasons for choosing the treatment rated as not relevant at all/ moderately relevant/ highly relevant
 - HbA1c lowering
 - Weight loss

- Cardiovascular risk reduction
- Favorable side effect profile
- Simple dosing / administration
- Guideline recommendation

[figure not shown]
6. Concomitant T2D medications (given as monotherapy or as fix combination with main T2D medication) at study index date 1
 - Metformin
 - Sulfonylurea
 - Acarbose
 - Pioglitazone
 - Insulin
 - others
7. Concomitant CVD and CKD medications at index date 1 (on class level only)
 - Antihypertensives ACEi or ARBs
 - Statins
 - Low dose aspirin
 - Beta blockers
 - Diuretics
8. Involvement of other HCPs in treatment decisions with regard to SGLT2i, DPP4i or GLP1a prescription at study index date 1 and with regard to discontinuation at index date 2 (yes/no; if yes, the medical specialty of the involved physician(s) should be specified)
9. Association of socioeconomic parameters with treatment decisions (such as employment status, family status, type of health insurance) at study index date 1
10. Status of T2D therapy approximately one year (\pm 2 months) after start
 - Stop date, if available
 - Reasons for discontinuation
 - Investigator's decision
 - Patient's request (difficulties in medication handling)
 - Patient's request (financial burden regarding co-payment)
 - Patient's request (other)
 - Lost to follow-up
 - Adverse event (in case of adverse reaction to empagliflozin or linagliptin or fatal adverse event, see [Section 11](#))
 - Death
 - Unknown
 - Other

Primary outcomes

- T2D patients' baseline characteristics when initiating either empagliflozin - or other SGLT2i, DPP4i or GLP1a on top of current antidiabetic treatment by different HCP specialties in CEE countries.

Secondary outcomes

- Burden of comorbidities (prevalence of CVD, CKD and CVD/CKD risk factors) in this T2D patient population at study index date 1
- Actual treatment use at study index date 1 in patients with and without established CVD (Established CV disease defined as acute myocardial infarction (AMI), cardiology intervention, ischemic heart disease (IHD), congestive heart failure (CHF), peripheral arterial disease (PAD), or stroke)
- To describe the association of socioeconomic parameters with treatment decisions at study index date 1
- To assess the discontinuation rate, reasons for discontinuation and average duration of treatment for GLP1a, DPP4i and SGLT2i after a follow up of approximately one year from the initial time point (= index date 2)

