Protocol for non-interventional studies based on existing data

| | |
|-----------------------------------|---|
| Document Number: | c24436488-02 |
| BI Study Number: | 1245-0187 |
| BI Investigational Product(s): | Jardiance® Synjardy® Trajenta® Jentadueto® |
| Title: | CORDIALLY® - CEE: Characteristics of patients with Type 2 Diabetes treated with modern antidiabetic drugs. A real-world data collection of patient baseline characteristics, treatment patterns and comorbidities in Central Eastern European (CEE) countries |
| Protocol version identifier: | 2.0 |
| Date of last version of protocol: | 12 Dec 2018 |
| PASS: | No |
| EU PAS register number: | EUPAS28505 Clinicaltrials.gov number: NCT03807440 |
| Active substance: | empagliflozin (ATC: A10BK03) linagliptin (ATC: A10BH05) |
| Medicinal product: | Jardiance® 10mg empagliflozin oral tablet Jardiance® 25mg empagliflozin oral tablet Synjardy® 5 mg empagliflozin 850 mg metformin oral tablets Synjardy® 5 mg empagliflozin 1,000 mg metformin oral tablets Synjardy® 12.5 mg empagliflozin 850 mg metformin oral tablets Synjardy® 12.5 mg empagliflozin 1,000 mg metformin oral tablets Trajenta® 5mg linagliptin oral tablet Jentadueto® 2,5mg linagliptin / 850 mg metformin oral tablet Jentadueto® 2,5mg linagliptin / 1000 mg metformin oral tablet |
| Product reference: | Jardiance EMEA/H/C/2677 Synjardy EMEA/H/C/3770 Trajenta EMEA/H/C/707 Jentadueto EMEA/H/C/2279 |
| Procedure number: | n.a. |
| Joint PASS: | No |
| Research question and objectives: | 
 1. To describe and compare T2D patients baseline characteristics when initiating either empagliflozin- or other SGLT2i, DPP4i or GLP1a on top of current antidiabetic treatment by different HCP specialties in CEE countries 2. To describe the burden of comorbidities (prevalence of CVD, CKD) and CVD/CKD risk factors in this T2D patient population at index date 1 3. To describe and compare the actual treatment at study index date 1 in patients with and without established CVD 
Established CV disease defined as acute myocardial infarction (AMI), cardiology intervention, ischemic heart disease (IHD), congestive heart failure (CHF), peripheral arterial disease (PAD), or stroke.
 |

| | |
|--|--|

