8.2 STUDY OBJECTIVES

The objective of the study is

1. To describe and compare T2D patients' baseline characteristics when initiating either empagliflozin - or other SGLT2i, DPP4i or GLP1a on top of current antidiabetic treatment by different HCP specialties in CEE countries
2. To describe the prevalence of comorbidities (prevalence of CVD, CKD) in this T2D patient population at index date 1
3. To describe and compare the actual treatment uses at index date 1 in patients with and without established CVD

Established CV disease defined as acute myocardial infarction (AMI), cardiology intervention, ischemic heart disease (IHD), congestive heart failure (CHF), peripheral arterial disease (PAD), or stroke.

4. To describe the association of socioeconomic parameters with treatment decisions at index date 1
5. To assess the discontinuation rate, reasons for discontinuation and average duration of treatment for GLP1a, DPP4i and SGLT2i after a follow up of approximately one year from the initial timepoint (= index date 2)

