9.5 STUDY SIZE

No formal sample size calculation is provided for this study. This NIS has been designed to describe, in a real-world setting, usage patterns and outcomes associated with empagliflozin or other SGLT2i or DPP4i or GLP1a in the clinical routine practice. The sample size of approximately 4000 patients is driven by the need to enroll an adequate number of patients to address the mentioned objectives, also across various subgroups, such as physician or country specific analyses. It is aspired to document at least 500 patients in the GLP1a and at least 1000 patients each in the SGLT2i and DPP4i subgroups. However, no formal limitations will be applied for recruitment of patients to subgroups with regard to medication of interest.

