5.2 SECONDARY OUTCOME(S)

- Burden of comorbidities (prevalence of CVD, CKD and CVD/CKD risk factors) in this T2D patient population at study index date 1
- Actual treatment use at study index date in patients with and without established CVD (Established CV disease defined as acute myocardial infarction (AMI), cardiology intervention, ischemic heart disease (IHD), congestive heart failure (CHF), peripheral arterial disease (PAD), or stroke)
- To describe the association of socioeconomic parameters with treatment decisions at study index date 1
- To assess the discontinuation rate, reasons for discontinuation and average duration of treatment for GLP-1 RA, DPP4i and SGLT2i after a follow up of approximately one year from the initial time point (= index date 2)

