7. PLANNED ANALYSES

All patients who have received a first prescription of respective study medication will be included in the analysis; this is the prescribed patient set. All analyses at index date 1 will be performed on the prescribed patient set and analyses at index date 2 will be performed on the full analysis set. If patients have missing values for an outcome, those patients will be excluded for that outcome's analysis.

The assessment will be carried out using SAS® software. The statistical characteristics presented in the end-of-text tables will be N / mean / SD / min / median / max for continuous variables. Tabulations of relative and absolute frequencies will be presented for categorical variables. Incidence rates and 95% CI will be given when appropriate. Subgroup analyses e.g. according to medication (i.e. empagliflozin or SGTL2i or DPP4i or GLP-1 RA), country and physician specialty are planned, as well as per history of CV disease. Descriptive analyses will be supplemented using χ^2 -test or Fisher's exact test for categorical variables and Wilcoxon-Mann-Whitney test for continuous variables. The analyses are purely explorative, hence no correction for multiple testing is needed.

The analyses will relate to the following data as recorded in the eCRF:

1. Patient demographics (age, gender, height, weight, BMI, ethnicity)
2. Time since diagnosis of Type 2 Diabetes
3. Clinical parameters relevant for T2D, CVD, CKD assessment as valid on index date 1
4. Presence of cardiovascular disease and related risk factors at index date 1
5. Presence of chronic kidney disease and related risk factors at index date 1
6. T2D medication the treating physician newly prescribes at study index date 1
7. Reason(s) for treatment decision at index date 1
8. Concomitant T2D medications at study index date 1
9. Concomitant CVD and CKD medications at index date 1
10. Other HCPs involved in treatment decisions at study index date 1 and at index date 2
11. Relevant socioeconomic parameters
12. Discontinuation rate, reason for discontinuation, duration of T2D therapy after one year (± 2 months)

All adverse events and adverse drug reactions collected per study protocol will be included and summarized in the final study report.

For the main analysis data from research question 1 to 5 will be evaluated in a descriptive manner for the total number of prescribed patients enrolled in the study.

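### Physical inactivity is defined with "or", so as written a patient who meets only one of the two exercise thresholds is classed as inactive

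*Protocol*

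**What the plan says.** Protocol 9.3.2, item 4, lists the risk factors for CVD and CKD at index date 1. Physical inactivity is a yes/no entry, "defined as less than 2.5 hours of moderate-intensity aerobic exercise or less than 75 minutes of vigorous aerobic exercise per week". This is the only definition of the item in either document.

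The item belongs to a secondary outcome, worded in SAP 5.2 as "Burden of comorbidities (prevalence of CVD, CKD and CVD/CKD risk factors) in this T2D patient population at study index date 1"; protocol 9.3.2 has the same outcome. Objective 2 on the protocol cover page also covers it: "To describe the burden of comorbidities (prevalence of CVD, CKD) and CVD/CKD risk factors in this T2D patient population at index date 1". Objective 2 in protocol 8.2 is narrower and leaves risk factors out: "To describe the prevalence of comorbidities (prevalence of CVD, CKD) in this T2D patient population at index date 1".

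SAP 7 analyses data as recorded in the eCRF and includes "Presence of cardiovascular disease and related risk factors at index date 1". It gives no derivation for inactivity. SAP 7.4 names CVD prevalence, CKD prevalence and SCORE, but not inactivity.

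**The concern.** The definition pairs one weekly threshold for moderate exercise (2.5 hours) with another for vigorous exercise (75 minutes). That pairing suggests two alternative ways of being active, in which case a patient is inactive only when neither is met. Joined by a disjunction, the rule does the opposite: failing either threshold is enough. A patient who walks briskly for 5 hours a week and does nothing vigorous is inactive. So is one who swims hard for 2 hours a week and does nothing moderate.

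Two things are at stake. If sites apply the wording literally, the reported prevalence is too high and may sit near its ceiling, which would hide real differences between groups. If some sites apply it literally and others by apparent intent, differences between countries or specialties may reflect how the item was read. SAP 7 plans subgroup analyses by medication, country, specialty and history of CV disease, and SAP 7.4 provides chi-square or Fisher tests for subgroup comparisons.

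Little downstream would catch the problem. The protocol lists no exercise minutes for collection, so the item cannot be re-derived at analysis. The eCRF checks in protocol 9.8 test completeness and plausibility, and no regular source data verification is planned. Protocol 9.12 relies on a standard eCRF and on training in the protocol, and training on this wording would pass the problem on.

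**Working it through.** The plan states no expected prevalence of inactivity, and protocol 9.5 says "No formal sample size calculation is provided for this study". There is therefore no figure to reproduce. The check is of the rule itself, followed by an illustration.

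**Step 1: the rule.** Let M mean that the patient reaches 2.5 hours of moderate exercise a week, and V that the patient reaches 75 minutes of vigorous exercise (both thresholds from protocol 9.3.2).

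| M | V | Inactive as written | Inactive if neither is met |
|---|---|---|---|
| no | no | yes | yes |
| yes | no | yes | no |
| no | yes | yes | no |
| yes | yes | no | no |

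The two rules differ in the two middle rows only.

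**Step 2: direction.**

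- As written: P(inactive) = 1 − P(M and V).
- Neither met: P(inactive) = 1 − P(M or V).
- Difference: P(M or V) − P(M and V) = P(exactly one threshold met).

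The difference cannot be negative. It is positive as soon as one patient meets exactly one threshold. This needs no outside data.

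**Step 3: size, under assumptions.** Every activity rate below is assumed; none comes from the documents.

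- Scenario A, with 35% meeting M, 8% meeting V and 5% meeting both: as written 1 − 0.05 = 0.95; neither met 1 − (0.35 + 0.08 − 0.05) = 0.62; gap 33 points.
- Scenario B, with 20%, 4% and 2%: as written 1 − 0.02 = 0.98; neither met 1 − (0.20 + 0.04 − 0.02) = 0.78; gap 20 points.
- Grid with M from 20% to 50% and V from 5% to 20%, independent, so the gap is pM + pV − 2·pM·pV. Lowest: 0.20 + 0.05 − 2(0.20)(0.05) = 0.23. Highest: 0.50 + 0.20 − 2(0.50)(0.20) = 0.50. Across the grid, prevalence is 90% to 99% as written and 40% to 76% under the neither-met rule.
- Same grid without independence: the gap is 0 when M and V are both 20% and are met by the same patients, and 0.50 + 0.20 = 0.70 when no patient meets both.

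Protocol 9.5 plans about 4000 patients. Gaps of 20 and 50 points would be 0.20 × 4000 = 800 and 0.50 × 4000 = 2000 patients classified differently, if every site read the item literally.

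**Step 4: reach.** Inactivity does not enter the definition of established CVD, and SCORE uses age, gender, systolic blood pressure, smoking and total cholesterol. No composite of risk factors is planned. Only the frequency of this item, and comparisons of it, are affected.

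**The case against.** The strongest reply is that nothing in the plan applies the rule mechanically. Site staff enter a yes or no from medical charts (protocol 9.4 and 9.10.2.2.1). A clinician may well take the phrase to mean that the patient reaches neither level, and if all sites did so there would be no bias. The wording that sites actually answered is in the eCRF, a stand-alone document under Annex 1 that is not available here. The documents also never say that either threshold suffices, and the item cites no source.

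Most of this stands. It makes the overstatement conditional on how sites read the item, and the intent remains an inference from the two intensity-specific thresholds. It does not clear the wording. In the same list, hypertension is defined so that one raised component is enough, and a site reading consistently would treat inactivity the same way. A mixture of readings is itself a defect, because it makes the item incomparable between sites.

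A reader might go further and infer that nearly every patient will be recorded as inactive, or that the whole risk-factor burden in objective 2 is overstated. The documents support neither. The first depends on activity rates that they do not give, and the second on a composite that is not planned.

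It is also fair that the analyses are declared exploratory and that a simple neither-met rule has its own gap. A patient with 2 hours of moderate and 60 minutes of vigorous exercise meets neither threshold, yet is clearly not idle. That bears on the fix, not on whether the current wording is wrong.

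**Conclusion.** The definition is wrong as written if, as the paired thresholds suggest, either one is meant to be enough. Applied literally, it classes as inactive everyone who meets only one threshold, and it overstates the prevalence of this risk factor by exactly that share. Applied unevenly, it produces inconsistent classification across sites and countries.

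The direction under literal reading follows from logic alone. The size does not: 20 to 50 percentage points is an illustration resting on assumed activity rates, most of it on independence of the two thresholds, and other overlaps on the same grid give 0 to 70. The true figure also depends on how many sites read the item literally, which the documents do not show.

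The effect is confined to one item of a secondary outcome. It should be corrected, but it does not threaten the study's main descriptive results.

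**What to change.** - In protocol 9.3.2, item 4, define inactivity as less than 2.5 hours of moderate **and** less than 75 minutes of vigorous aerobic exercise per week. Make the same change in the eCRF item if it carries the same wording.
- State how a mixture of moderate and vigorous activity is counted when neither threshold is met alone.
- Put the rule in the SAP, which has none for this item.
- For entries already made, query sites where charts hold enough detail on exercise. Otherwise report the wording that sites used, label the item as site-reported, and do not interpret subgroup differences in it.

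The wording change is one word, plus a sentence on mixed activity and a SAP entry. The queries are the real cost. Protocol 6 planned the end of data collection for Q1 2021 and SAP version 3.0 is dated 25 May 2021, so on that schedule most or all records were entered under the present wording. Charts from late 2018 may not record exercise by intensity, and for those records reporting the limitation is the realistic course.

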9.3.3 Covariates

Not applicable

9.4 DATA SOURCES

Data will be collected retrospectively from existing patient data (Medical chart review) previously documented by Health care professionals during routine practice in patients treated for T2D in an endocrinologist, diabetologist or cardiologist office-based setting (nonhospital). Medical records of patients meeting inclusion/exclusion criteria and having provided written informed consent will be used to collect all study data. The delegated site personnel of the participating sites will enter the relevant parameters into the electronic Case Report Forms (eCRF) in a timely manner. This method has been chosen as method of data collection as systematic diabetes registries do not exist in CEE countries.

Patients who are potentially eligible for study participation will be contacted by the delegated site personnel by phone or by sending a letter, inviting the patient to the next routine visit. In addition, patients will be informed about the study project and his/her potential eligibility for participating into the study.

9.5 STUDY SIZE

No formal sample size calculation is provided for this study. This NIS has been designed to describe, in a real-world setting, usage patterns and outcomes associated with empagliflozin or other SGLT2i or DPP4i or GLP1a in the clinical routine practice. The sample size of approximately 4000 patients is driven by the need to enroll an adequate number of patients to address the mentioned objectives, also across various subgroups, such as physician or country specific analyses. It is aspired to document at least 500 patients in the GLP1a and at least 1000 patients each in the SGLT2i and DPP4i subgroups. However, no formal limitations will be applied for recruitment of patients to subgroups with regard to medication of interest.

